Topical photodynamic therapy (PDT) is widely used to treat superficial non-melanoma skin cancer (NMSC) and dysplasia, notably actinic keratosis and may also be effective in a range of other dermatological conditions. A major limitation of PDT is pain during irradiation, which occurs in most and can be severe in ~20% of patients. A lack of knowledge of the mechanism of PDT-induced pain has limited the development of effective approaches for prevention or relief of this adverse effect. We developed a mouse model of PDT-induced pain that enabled us to determine the molecular mechanisms involved. Use of the model in combination with an *in vitro* assay of PDT-induced excitation of nociceptive neurons led to our identification of menthol as a potential analgesic agent for minimising PDT-pain. This proposal describes the prospective randomised double blind, placebo controlled clinical trial we will undertake in which we investigate the use of topical menthol for PDT-induced pain relief in patients with actinic keratosis of the face and scalp who will be attending general dermatology and PDT outpatient clinics at Ninewells Hospital, Dundee.

This will be undertaken by comparison of 5% menthol in aqueous cream with aqueous cream as placebo and the primary outcome measures will be pain recorded on a visual analogue scale (VAS) during and up to 24 h after PDT. Secondary outcomes are phototoxicity, assessed by a semi-quantitative scoring system immediately after PDT, fluorescence assessed routinely after cream application and before irradiation and outcome based on clinical assessment three months after PDT and patient evaluation. Patients will be involved in the study from the first visit for PDT until the three-month assessment visit after PDT. Data analysis will be undertaken using within-subject paired analyses as patients act as their own control. Information from this study will inform us as to whether we should or should not incorporate topical menthol into PDT treatment regimens routinely in order to reduce pain and increase tolerance of treatment. The information will also provide us with additional information as to the mechanisms of PDT-induced pain and its possible prevention and/or relief.

1.0 INTRODUCTION

1.1 BACKGROUND

Overview of background and purpose to the study

Topical photodynamic therapy (PDT) is widely used to treat superficial non-melanoma skin cancer (NMSC) and dysplasia, notably actinic keratosis (AK) and may also be effective in a range of other dermatological conditions [1, 2].

Topically applied 5-aminolaevulinic acid (ALA), or its methyl ester (MAL), is absorbed (preferentially by diseased skin) and metabolised to the photosensitiser, protoporphyrin IX (PpIX) [3]. Irradiation during PDT causes photobleaching of PpIX and production of reactive oxygen species (ROS), particularly singlet oxygen, initiating cell destruction. A major limitation of PDT and the primary reason for lack of successful treatment delivery and refusal of therapy is pain during irradiation, which occurs in most and can be severe in ~20% of patients [3, 4]. A lack of knowledge of the mechanism of PDT-induced pain has limited the development of effective

A randomised double blind, placebo controlled study of the efficacy of topical menthol for pain relief during topical photodynamic therapy

v.6.0 27/March/2019

approaches for prevention or relief of this adverse effect [3-5]. The use of low irradiance light delivery may limit pain but requires prolonged treatment times and is only applicable in specific situations and is not feasible for most patients treated with PDT [6, 7]. It is also unclear whether the choice of photosensitiser pro-drug influences pain severity. Clinical studies suggest that MAL use is either associated with less severe PDT-induced pain than the use of ALA [4, 8, 9] or that there is no difference between treatments [10, 11]. The European Medicines Agency has recently approved Ameluz® (BF-200 ALA) for PDT of AK of the face and scalp [12]. Ameluz® is a nanoemulsion containing 8% ALA-HCl, with improved stability. In a recent study 82% of patients experienced pain during Ameluz® PDT but this was not significantly different to MAL PDT [11]. We developed a mouse model of PDT-induced pain that enabled us to determine the molecular mechanisms involved. Use of the model in combination with an *in vitro* assay of PDT-induced excitation of nociceptive neurons led to our identification of menthol as a potential analgesic agent for minimising PDT-pain (see below). It is essential that we now determine whether the topical application of menthol is effective for PDT-induced pain relief in patients treated with PDT as this is a simple, safe approach that could easily be routinely incorporated into PDT regimes and if effective would markedly improve the management of such patients. Thus, this proposal describes the prospective randomised double blind, placebo controlled clinical trial we will undertake in which we investigate the use of topical menthol for PDT-induced pain relief in patients with AK of the face and scalp.

Pain associated with PDT

Most patients receiving PDT experience pain during irradiation. In Dundee, 16% of 4717 PDT treatments were associated with severe pain [4]. This limits successful and effective delivery of PDT and negatively impacts on the patient's experience of treatment. Unsurprisingly, given the nature of pain transmission, PDT is most painful in patients when performed on highly innervated skin such as the face and scalp [5, 13]. Interestingly, higher pain levels are experienced during PDT for AK and psoriasis than for basal cell carcinoma [13, 14], perhaps implicating neuromodulatory factors released from specific cell types. Characteristics of irradiation (emission spectrum and irradiance) appear to influence the perception of pain. Red light produces more pain than violet light and pain appears to correlate with the rate of photobleaching of PpIX [15, 16]. Reduction of irradiance may reduce pain but greatly increases treatment times [6, 7]. Other options for pain relief are limited as conventional non-invasive methods, such as topical analgesia with morphine or local anaesthetics are not significantly effective [5, 17, 18]. Local anaesthetic nerve block results in effective pain reduction [19] but is invasive, not feasible at all body sites and there may be risk of toxicity. Cooling is associated with slight reduction in PDT-induced pain [20], although there are concerns that this may reduce the efficacy of PDT [21].

Mechanisms of PDT pain

A randomised double blind, placebo controlled study of the efficacy of topical menthol for pain relief during topical photodynamic therapy

v.6.0 27/March/2019

Little is known about the mechanism(s) of PDT-induced pain. At the time of writing a literature search using the terms “pain and photodynamic therapy” yielded 423 publications, although most relate to the prevalence of PDT-pain and the limited success of treatment. Inhibition of PDT-induced pain by nerve block [19] implicates classical modes of pain transmission in which voltage activated sodium channels (VASCs) are activated leading to action potentials in primary afferent fibres stimulating ascending pain pathways in the spinal cord, thalamus and cortex [22]. PDT pain is described as a burning sensation. Furthermore, demonstrations that cooling reduces PDT pain may implicate heat-sensitive nociceptors. The transient receptor potential (TRP) family of ion channels senses heat, among other noxious stimuli including the pungent vanilloid capsaicin [23].

The heat/capsaicin activated TRP channel is TRPV1 [24] and this channel is a candidate for mediating PDT pain. However, PDT causes only modest temperature increases below the threshold for TRPV1 under normal conditions [24, 25] (Figure 1; Appendix 1) and thus there remains uncertainty about mechanisms involved.

Pre-clinical Pilot Studies

In pilot studies, we identified an electrophysiological correlate of PDT-evoked pain in cultured mouse primary afferent DRG neurons and developed a behavioural model for this phenomenon (Figures 2-9; Appendix 1).

PpIX phototoxicity-induced pain behaviour in mice

We examined the effect of laser irradiation (630 nm, 3.7 J/cm²) and ALA applied topically (4-6 h) to the tails of NIH SWISS mice. Neither topical ALA (n = 35), nor laser irradiation alone (n = 30), caused discernible pain behaviour in either mouse strain. By contrast, 20 ± 3 s (n = 30) of tail lifting, holding and licking occurred during 60 s following laser irradiation of ALA treated tails (Figure 2a; Appendix 1). Pain behaviour ceased within 5 minutes suggesting that the underlying pain was acute and transient. Tail lifting, holding and licking did not occur in the 60 s period following irradiation in mice treated with vehicle cream. We observed PpIX emission non-invasively using fluorescence spectroscopy with fibre-optic coupled laser excitation at 405 nm (Figure 2b; Appendix 1). Compared to vehicle treated mouse tails, the characteristic PpIX emission spectrum was enhanced by ALA treatment to levels similar to those achieved in the ALA treated human forearm (Figure 2b; Appendix 1). The *in vivo* data demonstrated that neither PpIX production nor laser irradiation alone was sufficient to generate pain in mice. By contrast, ALA PDT was associated with quantifiable pain behaviour.

PpIX phototoxicity evokes action potentials in DRG neurons

Primary afferent dorsal root ganglion (DRG) neurons transmit nociceptive pain from peripheral sites, such as the tail, to the spinal cord. We dissociated DRG from mice and performed flow cytometry on cells grown for 7 days *in vitro*. Flow cytometry revealed that cells treated with ALA (1 mM for 4 h) produced PpIX fluorescence that was not seen in untreated cells (Figure 3a; Appendix 1). We examined responses of

A randomised double blind, placebo controlled study of the efficacy of topical menthol for pain relief during topical photodynamic therapy

v.6.0 27/March/2019

small DRG neurons (<25 μm) to ALA either alone or in combination with laser irradiation (630 nm) using the cell attached configuration to record action potentials. This approach preserves the intracellular milieu while action potentials are acquired as a combination of resistive and capacitive currents [26]. Spontaneous action potentials occurred very rarely in recordings from DRG neurons (grown for 1-15 days *in vitro*) under control conditions or in recordings from neurons exposed to ALA (1 mM, 4-7 h) prior to irradiation (Figure 3b; Appendix 1). By contrast, during laser irradiation (630 nm) neurons exposed to ALA exhibited bursts of frequent action potentials (Figure 3b; Appendix 1).

While 97% of neurons responded to PpIX irradiation (day 4-15 *in vitro*), there was considerable variability in the latency to the first burst of action potentials (486 ± 20 s, $n = 135$), which equates to a mean light dose of 47 ± 2 J/cm² required to evoke a response. The instantaneous frequency of action potentials was 11.6 ± 1.3 Hz (day 7 *in vitro*). The mean frequency of firing during the entire period of irradiation was 0.23 ± 0.03 Hz. Interestingly, despite the known cellular toxicity of PpIX irradiation, resulting from the release of ROS, most DRG neurons survived the full 1200 s of laser exposure.

Using the whole-cell current-clamp recording configuration we examined the effects on membrane potential of ALA and irradiation either alone or in combination (Figure 3c; Appendix 1). DRG neurons exhibited infrequent spontaneous action potentials under control conditions. Neither ALA (-57 ± 3 mV, $n = 7$) nor laser irradiation alone (-60 ± 3 mV, $n = 5$) affected resting membrane potential or frequency of spontaneous action potentials (Figure 3c; Appendix 9). However, laser irradiation of ALA treated (4-7 h) DRG neurons led to sustained depolarisation (of 9 ± 1 mV, $n = 3$) and the appearance of frequent action potentials (Figure 3d; Appendix 9).

Taken together, the *in vitro* data demonstrate that neither PpIX production nor laser irradiation alone was sufficient to generate action potentials in nociceptive neurons. By contrast, PpIX irradiation depolarized neurons and initiated bursts of action potentials.

Menthol suppresses PpIX phototoxicity-evoked action potentials and pain

Menthol exhibits local anaesthetic effects through inhibition of VASCs on nociceptive neurons [27]. Menthol also causes a cooling sensation by activating TRPM8 receptors [28]. Both of these actions could provide analgesia to patients being treated with PDT. We examined whether menthol (300 μM and 600 μM) inhibited ALA PDT-induced action potentials recorded from DRG neurons.

Menthol inhibited action potential frequency in a concentration-dependent manner (Figure 4a; Appendix 1). Also, the percentage of cells that responded to PDT was reduced by menthol (600 μM) from 100% to 33%. Menthol (300 μM) had no effect on the threshold light dose; however, the reduction in the number of cells responding in

A randomised double blind, placebo controlled study of the efficacy of topical menthol for pain relief during topical photodynamic therapy

v.6.0 27/March/2019

the presence of 600 µM menthol precluded analysis of the average threshold light dose in this case.

We next investigated whether menthol influenced ALA PDT-induced pain behaviour in mice. The application of menthol (16%) in aqueous cream had no effect on PpIX-mediated fluorescence determined using the photospectrometer with fibre-optic coupled laser excitation at 405nm (Figure 4b; Appendix 1). The application of menthol (2% and 16%) to the tails of mice 600s prior to laser (630 nm, 3.7 J/cm²) irradiation caused a dose-dependent reduction in the duration of pain behaviour (Figure 4c; Appendix 1). These data suggest a role for TRP pathways [29] and indicate that menthol is an effective analgesic for treating ALA PDT-induced pain in mice and we will now investigate this in patients receiving PDT for AK.

1.2 RATIONALE FOR STUDY

As menthol is such a well-tolerated and safe treatment we would envisage that if the clinical study supported the *ex-vivo* findings and did indeed significantly reduce PDT-induced pain, then this would be routinely incorporated into PDT treatment protocols and significantly improve patient care and the tolerance of PDT. We will use 5% menthol as this is available for clinical use and in order not to miss a potential pain-relieving effect.

2 STUDY OBJECTIVES

2.1 OBJECTIVES

2.1.1 Primary Objectives

The primary objective of this study is to examine whether the pain (as assessed by VAS pain scores) of topical PDT is significantly different when using menthol in aqueous cream applied before PDT compared with aqueous cream (placebo) application before PDT.

2.1.2 Secondary Objectives

We will also examine possible differences in phototoxicity of the two regimens and assess patient evaluation of treatment. We will additionally assess fluorescence after cream application and before irradiation, using Wood's light as used in routine clinical practice. Efficacy of the two treatment regimens will also be assessed.

2.2 OUTCOMES

2.2.1 Primary Outcomes

Pain will be assessed by the patient using a visual analogue scale of 0-10 cm. Maximal recall of pain experienced during PDT will be recorded immediately after PDT, and then pain scores at three, six and 24 hours after PDT. The patient-scored pain at the first time point will be undertaken with the aid of a blinded investigator and subsequently the patient alone will assess symptoms.

A randomised double blind, placebo controlled study of the efficacy of topical menthol for pain relief during topical photodynamic therapy

v.6.0 27/March/2019

2.2.2. Secondary Outcomes

Phototoxicity as assessed by semi-quantitative scoring of erythema, oedema and urticaria will be assessed immediately after irradiation. Fluorescence will also be assessed after Ameluz and IMP applications using Wood's light. Efficacy of treatment (clearance, partial or no response) three months after PDT will be determined clinically. Patient evaluation of treatment will also be assessed.

3 STUDY DESIGN

3.1 STUDY DESCRIPTION

This protocol describes a prospective, single site, randomised, double blind placebo controlled study to assess the efficacy of menthol in aqueous cream for PDT-induced pain. Each subject will act as their own control. Potential participants with a diagnosis of actinic keratosis (AK) bilaterally affecting face or scalp who are referred for PDT will be identified by the Chief Investigator (CI), a consultant dermatologist, screening referrals and will be invited to participate by letter and a patient information sheet (PIS) will be sent out with the PDT clinic appointment details. Patients will also be identified in the dermatology outpatient or PDT clinics by either a dermatologist, specialist nurse or technologist and will be provided with details of the study and a PIS. At first visit at the PDT clinic the study will be described in full detail by a PDT study doctor, technologist or clinic nurse and written informed consent will be obtained prior to any study-related activities. Computer-generated block randomisation of the active/placebo to right or left sides and which side will be treated first will be undertaken by Tayside Pharmaceuticals. Patients will then receive their randomised treatment and this will also be undertaken by the Photobiology Technician or nurse as is the normal clinical practice in the PDT Unit.

A study clinician, technologist or nurse will obtain a medical history and the areas for treatment will be examined, the study fields will be marked out, lesions counted and the fields mapped and photographed. The maximal diameter of each comparable field will be 5x10cm. Topical PDT will be undertaken using the standard Ameluz[®] PDT regime (11). In brief, any hyperkeratotic areas will be surface prepared using a disposable ring curette (Stiefel[™]), without the need for local anaesthesia. Ameluz[®] gel will be thinly applied to both comparative fields, left to dry and occluded for three hours with Tegaderm and Mepore dressings. After removal of the dressings and surplus gel, the active treatment (menthol 5% in aqueous cream) or placebo (aqueous cream) will be applied to right/left side according to randomisation. The IMPD/placebo will be provided as 1g in 2mL syringes, applied to the maximum field size field of 5x10cm or pro-rata to smaller field sizes. Ten minutes later any excess cream will be wiped off and irradiation will commence (LED 37.5 J/cm², irradiance approximately 80 mW/cm²), with the randomisation to account for which side will be treated first. Menthol vapour will be in the room in order to mask the vapour of the IMP and to aid with ensuring blinding of both patient and assessor (research nurse or another technologist).

Assessments

Fluorescence will be examined using a semi-quantitative scoring system (0=none; 1=minimal; 2=moderate; 3=strong) after 3 h of Ameluz application and after menthol/placebo application.

Pain scores will be recorded by the patient immediately after irradiation (as recall of maximal pain experienced during irradiation) and at 3, 6 and 24 h after irradiation

A randomised double blind, placebo controlled study of the efficacy of topical menthol for pain relief during topical photodynamic therapy

[figure not shown]
v.6.0 27/March/2019

using a VAS score of 0-10cm at each time-point. The study technologist or research nurse will be present at the time of the first pain score but patients will fill in the VAS scores themselves at home for the 3, 6 and 24 h time-points and send these back to the PDT clinic by stamped addressed envelope. A study nurse will contact the patient by phone at one week, to ask about any adverse effects and to check that the VAS scores are returned.

Phototoxicity will be assessed by the study technologist or research nurse immediately after irradiation using a semi-quantitative scoring system for erythema (0=none; 1=mild; 2=moderate; 3=severe), oedema (1=yes; 0=no), exudation (1=yes; 0=no) and urticaria (1=yes; 0=no).

[figure not shown]
Efficacy will be assessed clinically approximately three months (\pm 2 weeks) after PDT, with clearance, partial response or no response recorded as outcomes. Patient evaluation of treatment and of blinding will also be assessed for each treatment site when the patient returns their pain scores after 24h, using the following two questions: [1] Which side do you think received menthol? Right/left/not sure; [2] Which side do you think was best? Right/left/no difference.

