5.5.2 Treatment Allocation

Patients will be allocated treatment to both right side and left side e.g. right side to receive treatment A; left side to receive treatment B. Patients should be unable to distinguish treatments by smell as menthol has a strong smell, which will likely permeate the air around the patient. In addition, menthol vapour will be present in the room so that there is an overall menthol smell, which will be difficult to localise.

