5.5.3 Blinding and Emergency Unblinding Procedures

Those assessing patients (Consultant Dermatologist, study technologist or research nurse) will not be aware of which side has received which intervention. It is possible that all patients (from sensation [cooling] of menthol) might not remain fully blinded. Patients will be instructed not to tell those assessing them if they suspect they know which intervention is applied to each side. After treatment, patients will be asked to provide an opinion as to which treatment was applied to each side to allow assessment as to how complete patient blinding was.

Given the nature of the study, it is very unlikely that unblinding will be required. If required, it will be conducted by a PBU member of staff unconnected to the trial.

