12.2 TRIAL MANAGEMENT

A Research Nurse will oversee the study and will be accountable to the CI. The Research Nurse will be responsible for checking the CRFs for completeness, plausibility and consistency. However, this will remain the overall responsibility of the CI. Any queries will be resolved by the CI or delegated member of the trial team.

A study-specific Delegation of Responsibilities & Signature Log will be prepared, detailing the responsibilities of each member of staff working on the trial.

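### Nothing in the plan keeps side-specific pain scores and the patient's written menthol guess from the roles that rate phototoxicity and three-month efficacy

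*Combined protocol and SAP*

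**What the plan says.** Section 5.5.3 states that the dermatologist, technologist and research nurse who assess patients will not know the allocation by side. It accepts that cooling may unblind some patients and adds a safeguard: "Patients will be instructed not to tell those assessing them if they suspect they know which intervention is applied to each side". Sections 3.1, 5.5.2 and 6.3 add menthol vapour in the room, and 5.5.1 conceals the randomisation code from investigators.

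Two data routes then matter.

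- **Day 1.** Section 3.1 says "Phototoxicity will be assessed by the study technologist or research nurse immediately after irradiation using a semi-quantitative scoring system". It also says "The study technologist or research nurse will be present at the time of the first pain score", and Section 2.2.1 says "The patient-scored pain at the first time point will be undertaken with the aid of a blinded investigator". Neither section gives the order of the two tasks or requires different people.
- **After Day 1.** Patients complete the 3, 6 and 24 hour VAS at home and "send these back to the PDT clinic by stamped addressed envelope". With these they answer two written questions: which side they think had menthol, and which side they think was best. A nurse phones at one week, partly "to check that the VAS scores are returned". Section 12.2 says "The Research Nurse will be responsible for checking the CRFs for completeness, plausibility and consistency". Section 12.1 gives oversight of data monitoring to a group made up of the chief investigator, the technologist and the research nurse. Efficacy is rated at about three months. Section 3.1 does not name the rater.

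**The concern.** The safeguard in 5.5.3 depends on assessors not learning what the patient suspects. The data flow in 3.1 and 12.2 puts that suspicion on paper and brings it to the clinic, and to a role on the assessor list, well before the last assessor-rated outcome. The vapour and the concealed code deal with smell and with the allocation list. They do not hide a pain score or a written guess.

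On Day 1, a person who helps with the first pain score may also grade erythema, oedema, exudation and urticaria on the same two fields. A rater who knows which side hurt more may grade that side more severely without thinking about allocation at all. If menthol reduces pain, such a halo would favour one arm consistently. At stake is whether phototoxicity and three-month response can show, free of rater expectation, that menthol leaves the PDT reaction and its efficacy unchanged or alters them.

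**Working it through.** **Step 1: reproduce the plan's sample size, to see what its SD means.** Section 9.1 gives a difference of 1.5 cm, an SD of 2 cm, a 5% level, 90% power and 21 subjects. It does not state sidedness; two-sided is assumed. For a paired t-test with n = 21 (df = 20), the noncentrality is 1.5/2 × √21 = 3.44 and the power is 90.5%. The smallest n reaching 90% is 21, and 21/(1 − 0.30) = 30 recruited. Both figures reproduce, so the plan uses 2 cm as the SD of the within-patient difference.

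**Step 2: how informative are the pain scores about the menthol side?** Let D be placebo-side pain minus menthol-side pain, assumed normal with mean δ and SD s. An assessor who sees both marks and takes the less painful side to be menthol is right with probability P(D > 0) = Φ(δ/s).

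Inputs: δ = 1.5 cm (Section 9.1) and 3 cm (interim, Section 9.2), with smaller values and zero for comparison; s = 2 cm (Section 9.1). As a sensitivity assumption, if 2 cm is instead the SD on each side with independent errors, s = 2 × √2 = 2.83 cm.

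| True effect δ | s = 2 cm | s = 2.83 cm |
|---|---|---|
| 0 cm | 50% | 50% |
| 0.5 cm | 60% | 57% |
| 1 cm | 69% | 64% |
| 1.5 cm | Φ(0.75) = 77% | Φ(0.53) = 70% |
| 3 cm | Φ(1.50) = 93% | Φ(1.06) = 86% |

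Among 21 completers with s = 2 cm, that is about 16 correct at 1.5 cm (21 × 0.773 = 16.2) and about 20 at 3 cm (21 × 0.933 = 19.6).

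**Step 3: what cannot be computed.** The documents give no figure for the accuracy of the written guess, nor for how far a rater would shift a score on knowing the likely side. The table therefore measures how much the pain scores reveal, not the bias that results.

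**Step 4: which outcome each route can reach.** Phototoxicity is scored on Day 1, so only the first pain score can influence it. The posted scores and guess can reach only the three-month efficacy rating. The VAS outcomes are the patient's own scores, so neither route alters them.

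**The case against.** Much of the opposing case stands.

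- **Same person.** A reader might infer that one individual watches the patient mark the VAS and then scores phototoxicity. The documents say only that the same roles may be present and assist. Section 3.1 allows either role for each task, and the study matrix in 3.3 assigns phototoxicity to a technician. Overlap is permitted, not stated.
- **Efficacy rater.** A reader might infer that this rater reads the returned forms. The clinic is only their postal destination, the rater is not named in 3.1, and 5.5.3 includes the dermatologist among the assessors. Access is again possible, not stated.
- **Inference of the side.** A reader might conclude that assessors can usually tell. That depends on menthol working. With no effect the pain scores carry no information about side, and any unblinding would come only through cooling, which 5.5.3 treats as a possibility. The protocol also lists hyperalgesia as a menthol effect (Section 10.2, Appendix 2), so a rater need not equate less pain with menthol.
- **Syringe code.** A reader might take "right side to receive treatment A; left side to receive treatment B" as a letter code common to all patients. The text gives it only as an example of one patient's allocation, and 6.1.4 specifies no label format. This does not support a concern.
- **Anchoring.** Three of the four phototoxicity items are yes/no, and lesions are counted, mapped and photographed at baseline. This limits rater drift but does not remove it.

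The gap itself remains: 5.5.3 sets out to keep the patient's suspicion from assessors, and no text keeps the written version from them.

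**Conclusion.** The concern holds as a gap in the blinding procedures, not as evidence that assessors will be unblinded. The plan allows assessor roles to see side-specific pain scores and, before efficacy is rated, the patient's written guess. At the plan's own design effects the pain scores would point to the menthol side in about 77% to 93% of patients, or 70% to 86% with the larger SD. This assumes normal differences and a rater who sees both marks and reads less pain as menthol. With no menthol effect the figure is 50%.

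The exposure is confined to phototoxicity and three-month efficacy, both secondary. The size of any resulting bias cannot be estimated from the documents. The change is worth making because it costs little and makes the safeguard in 5.5.3 effective.

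**What to change.** Amend Sections 3.1 and 5.5.3 as follows.

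1. The patient marks the first VAS out of sight of whoever scores phototoxicity and places it in a sealed envelope, with no delay to the immediate pain score. Any help under 2.2.1 is limited to explaining the scale beforehand if the helper also scores phototoxicity.
2. The home VAS scores and the menthol and best-side answers come back sealed, or are held in a separate CRF section. They are withheld from whoever rates three-month efficacy until that rating is recorded. The Day 1 envelope is treated the same way.
3. Return and completeness checks on these forms, including the relevant part of the CRF check in 12.2, are done by someone who does not rate efficacy. The interim analyst in 9.2, already required to be outside treatment and assessment, can receive the pain data.

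The cost is slightly more form handling. Two alternatives are less attractive. Scoring phototoxicity on both fields before any pain score could delay recall for the first field by a second irradiation, about 37.5/0.080 = 469 seconds, at the time point that 5.5.1 ranks highest. Requiring different people for the two Day 1 tasks might need an additional member of staff.
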